2.0 Protocol Synopsis

TITLE:

A Randomized Controlled Trial Comparing Blood Glucose Control Intraoperative Between Insulin Drip vs. Insulin Boluses

SPONSOR

No sponsor for this study

FUNDING ORGANIZATION

King Faisal Specialist Hospital & Research Center-Jeddah

NUMBER OF SITES

Only (King Faisal Specialist Hospital & Research Center-Jeddah)

RATIONALE:

This randomized controlled trial will provide valuable information on the optimal method for achieving blood glucose control intraoperatively. The results of this study may help improve patient outcomes and reduce the incidence of postoperative complications.

STUDY DESIGN:

Randomized Controlled Trial

PRIMARY OBJECTIVE:

Is to compare blood glucose control intraoperatively between patients who receive insulin drip and patients who receive insulin boluses during adult cardiac surgery.

SECONDARY OBJECTIVES:

Is to evaluate the incidence of hypoglycemic events and the need for insulin adjustments during surgery.

PRIMARY OUTCOME:

rate of severe hypoglycemia

SECONDARY OUTCOME:

-duration of ICU stay
-lactate clearance

-wound infection day 7; and day 30 (clinic follow-up)

NUMBER OF SUBJECTS:

If you assume that 6% of the participants receiving boluses will acquire a wound infection and 1% of the participants receiving insulin drip will acquire an infection, you will need to enroll the following number of participants in your study to detect this difference:

Assuming a two-sided test and an alpha = 0.05, to have power = 80% to detect the difference, you need to enroll 192 participants per group for a total of 384 participants.

SUBJECT SELECTION CRITERIA:

Inclusion Criteria:

- All adult patients (above 18 y of age undergoing Cardiac surgery with preoperative blood glucose level (80 -180 mg/dL)
- Patient with History of diabetes and those taking antidiabetic medications.

Exclusion Criteria:

- Patients with known allergy or insulin intolerance.
- Patients with severe hepatic Dysfunction.
- Patient with History of hypoglycemic events in the past 6 month prior to surgery.

TEST PRODUCT, DOSE, AND ROUTE OF ADMINISTRATION:

Insulin drip will be administered at a starting rate of 2 units/hour and titrated to maintain blood glucose levels between 80-180 mg/dL.

CONTROL PRODUCT, DOSE AND ROUTE OF ADMINISTRATION:

Insulin boluses will be administered every 30 minutes to maintain blood glucose levels between 80-180 mg/dL.

DURATION OF SUBJECT PARTICIPATION AND DURATION OF STUDY:

Data will be collected 24 hours before the surgery, then patients will be followed up immediately, one week after, one month, 6 months and one year. Overall study duration is estimated to be 4 years.

CONCOMITANT MEDICATIONS.

No concomitant medications

EFFICACY EVALUATIONS.

SAFETY EVALUATIONS.

Since both methods of insulin delivery are already in use and FDA approved there is no safety concerns at the time being. However, an interim analysis will be carried out throughout the hospital stay and in each visit in the first postoperative year.

PLANNED INTERIM ANALYSES.

An interim analysis will be carried out throughout the hospital stay and in each visit in the first postoperative year.

STATISTICS. Analysis plan:

Using relative risk for statistical analysis and log rank. A P value of less than 0.05 will be considered statistically significant. Statistical analyses will be carried out using the SPSS or SAS.

Rationale for Number of Subjects:

Sample size calculated basis of a two-sided test and an alpha = 0.05, to have power = 80%. The results will be presented as mean (SD), median (interquartile (range), or proportion.

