3.0 Main Protocol

BACKGROUND

General Overview:

Hyperglycemia during surgery has been linked to increased risk of postoperative complications, including wound infections, delayed wound healing, and cardiovascular events. Maintaining blood glucose within a target range during surgery has been shown to reduce the incidence of these complications. Two methods commonly used for maintaining blood glucose control intraoperatively are insulin drip and insulin boluses. However, the optimal method for achieving blood glucose control remains unclear. Therefore, we propose a randomized controlled trial to compare blood glucose control intraoperative between two groups using insulin drip in one group and insulin boluses in the other group.

Methodology

Inclusion criteria:

- All adult Diabetic patients (Both type I & Type II) undergoing Cardiac surgery with preoperative blood glucose level (80 -180 mg/dL)
- Patient with History of diabetes and those taking antidiabetic medications.

Exclusion criteria:

- Patients with known allergy or insulin intolerance.
- Patients with severe hepatic Dysfunction.

- Patient with History of hypoglycemic events in the past 6 month prior to surgery.

Randomization:

Simple randomization will be used for randomization. The participants will be randomized into two groups based on methods of insulin delivery.

- Group A: Insulin drip will be administered at a starting rate of 2 units/hour and titrated to maintain blood glucose levels between 80-180 mg/dL.
- Group B: Insulin boluses will be administered every 30 minutes to maintain blood glucose levels between 80-180 mg/dL.

Insulin boluses will be considered as a control group.

Statistical analysis:

The results will be presented as mean (SD), median (interquartile (range), or proportion. Using relative risk for statistical analysis and log rank. A P value of less than 0.05 will be considered statistically significant. Statistical analyses will be carried out using the SPSS or SAS.

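### The primary objective is intraoperative glucose control, but no listed outcome measures glucose within or above 80-180 mg/dL; the primary outcome counts only severe lows.

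*Protocol*

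**What the plan says.** The title, the rationale, the primary objective and the Background all pose the same question. The rationale in the Synopsis reads "This randomized controlled trial will provide valuable information on the optimal method for achieving blood glucose control intraoperatively". The primary objective reads "Is to compare blood glucose control intraoperatively between patients who receive insulin drip and patients who receive insulin boluses during adult cardiac surgery". The Background in section 3.0 says "we propose a randomized controlled trial to compare blood glucose control intraoperative between two groups" and gives the reason: "Maintaining blood glucose within a target range during surgery has been shown to reduce the incidence of these complications". It names hyperglycemia as the harm to be avoided.

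The secondary objective reads "Is to evaluate the incidence of hypoglycemic events and the need for insulin adjustments during surgery".

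The Synopsis then lists four outcomes. The primary outcome is "rate of severe hypoglycemia". The secondary outcomes are ICU stay, lactate clearance, and wound infection at days 7 and 30. Both arms are managed to 80-180 mg/dL (Synopsis; sections 3.0 and 4.4).

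The sample size of 192 per arm (384 in total) rests on wound infection: "If you assume that 6% of the participants receiving boluses will acquire a wound infection and 1% of the participants receiving insulin drip".

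**The concern.** The main question is about control within a range, but the main measure looks at one extreme. Severe hypoglycemia is part of glucose control, and the protocol itself places hypoglycemic events under the secondary objective. The Background's own reason for the trial, staying in range and avoiding high glucose, has no glucose outcome at all.

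The stake is the conclusion the trial can draw. If severe lows are equally frequent in the two arms, they tie on the primary outcome even if one spends more of surgery above 180 mg/dL. A report of no difference would then be read as equal glucose control, which the trial would not have measured. The protocol also plans that "an interim analysis will be carried out throughout the hospital stay and in each visit in the first postoperative year". A glucose measure chosen after such looks would be open to selection.

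**Working it through.** **1. Outcomes against the protocol's own range.** The limits of 80 and 180 mg/dL make three zones.

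| Listed outcome | Below 80 | 80-180 | Above 180 |
|---|---|---|---|
| Severe hypoglycemia (primary) | severe part only | no | no |
| ICU stay | no | no | no |
| Lactate clearance | no | no | no |
| Wound infection | no | no | indirect only |

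The four outcomes measure part of one zone and neither of the other two.

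**2. Does later text repair this?**
- The efficacy-evaluations heading in the Synopsis has no content under it.
- Section 5.1.1 schedules blood sugar monitoring for the first postoperative day and the hospital stay, not for surgery.
- Section 6 names blood sugar as a safety assessment, without an outcome.
- The data lists in 5.1.1 and 8.1 name intraoperative lactate, preoperative fasting glucose and HbA1c, but not intraoperative glucose. Their general wording on surgery and hospital course, or the data management plan in 8.2, may cover it. Collecting a value does not make it an outcome.

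**3. What the stated 192 is for.** Inputs from the Synopsis: 6% versus 1% wound infection, two-sided alpha 0.05, power 80%, equal arms. The likelihood-ratio chi-square formula is

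n = (1.960 + 0.842)² / {2 × Σ[pᵢ ln(pᵢ/p̄) + (1−pᵢ) ln((1−pᵢ)/(1−p̄))]}, with p̄ = 0.035.

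The sum is 0.0323 − 0.0247 − 0.0125 + 0.0253 = 0.0205 (0.02046 before rounding), so n = 7.85 / 0.0409 = 191.8, rounded up to 192. The plan's figure is reproduced, but for a secondary outcome. The pooled normal approximation would give 211 for the same inputs.

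**4. What 192 per arm gives for the stated primary outcome.** The protocol gives no rate of severe hypoglycemia, so the rates below are assumed. Pooled normal approximation:

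power = Φ{[d − 1.960 √(2p̄(1−p̄)/192)] / √([p₁(1−p₁)+p₂(1−p₂)]/192)}.

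For 2% versus 1%: d = 0.01 and the two standard errors are 0.01241 and 0.01240, so power = Φ[(0.01 − 0.02432)/0.01240] = Φ(−1.155) = 12%.

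| Assumed rates | Power, normal approximation | Exact, uncorrected chi-square | Exact, Fisher | n per arm for 80% |
|---|---|---|---|---|
| 2% vs 1% | 12% | 11% | 4% | 2319 |
| 4% vs 2% | 21% | 20% | 12% | 1141 |
| 10% vs 5% | 46% | 47% | 39% | 435 |

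Solving the same formula for 80% power at 192 per arm gives detectable pairs of 6.4% vs 1%, 8.3% vs 2% and 13.2% vs 5%.

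**5. What 192 per arm gives for a continuous control measure.** For a patient-level measure such as the proportion of readings in range, the detectable difference is (1.960 + 0.842) × √(2/192) = 0.286 SD at 80% power. The protocol gives no SD, so this cannot be turned into percentage points.

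**The case against.** Severe hypoglycemia is a facet of glucose control. With both arms managed to one range, a safety-oriented marker is a defensible primary outcome. It is also not identical to the hypoglycemic events of the secondary objective: the primary outcome is limited to severe events and has no stated time window, whereas the objective concerns events during surgery. The high side has an indirect, patient-relevant check in wound infection, which the Background links to hyperglycemia. Blood sugar is monitored after surgery and listed for safety, and the protocol plans means and medians. The documents give no figure for how often either arm would run high, so the harm is hypothetical. The power figures rest on assumed rates and bear on the sample size more than on the missing outcome.

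Most of this is fair as a limit on the claim. The primary outcome is a partial measure, not an irrelevant one, and high drift is unquantified. But postoperative monitoring and a safety listing do not supply an intraoperative outcome, and wound infection cannot show which method kept glucose in range. An SAP could say how an outcome is calculated; which outcome answers the primary objective belongs in the protocol.

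**Conclusion.** The concern holds, and it must be fixed. Followed as written, the trial answers its primary question only for severe lows; glucose in range and above 180 mg/dL goes unmeasured by any outcome. The primary objective, the primary outcome and the endpoint behind the sample size are three different things. This rests on the protocol's wording and needs no assumption.

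The power consequences do rest on assumed rates. With severe hypoglycemia as primary, 192 per arm detects only large differences unless severe lows are common: halving a 2%, 4% or 10% rate has about 12%, 21% or 46% power. A continuous in-range measure would be sensitive to about 0.29 SD, on a normal approximation and an SD the protocol does not give.

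**What to change.** 1. **Add named outcomes.** Suggested text: *Secondary outcomes (added): each patient's proportion of intraoperative blood glucose readings within 80-180 mg/dL; each patient's proportion of intraoperative readings above 180 mg/dL.* Name intraoperative glucose (value and time) in 5.1.1 and 8.1. Because such proportions depend on when and how often readings are taken, record them on the same schedule in both arms, at an interval the investigators set.
2. **Align the primary pair before any comparative data are seen.** The investigators choose between two options.
   - (a) Make the in-range proportion the primary outcome and severe hypoglycemia the main safety outcome.
   - (b) Restate the primary objective as a comparison of the rate of severe hypoglycemia between drip and boluses, adjust the title and rationale to match, and keep the in-range and high-side outcomes as secondary.
3. **In either case, state what 192 per arm delivers** for the chosen primary outcome, with the assumed rate or SD.
4. **Minor:** the secondary objective's need for insulin adjustments has no outcome. Give it one or remove it.

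The cost is an outcome amendment, a few CRF fields and a restated sample-size justification. Glucose readings are already needed to manage patients to the range. Option (a) demotes severe hypoglycemia from primary. Option (b) leaves the title's present question to a secondary outcome and accepts the limited power shown above. Step 1 alone closes the measurement gap but leaves the primary outcome under the secondary objective.

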7.1 Sample size

This study will include a total of 384 adult patients randomly assigned to each arm (192 per arm).

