7.3 Overall statistical and analytical plan

This study will include a total of 384 adult patients randomly assigned to each arm (192 per arm). Sample size calculated basis of a two-sided test and an alpha = 0.05, to have power = 80%. The results will be presented as mean (SD), median (interquartile (range), or proportion. Using relative risk for statistical analysis and log rank. A P value of less than 0.05 will be considered statistically significant. Statistical analyses will be carried out using the SPSS or SAS.

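### The sample size and 80% power are for wound infection, a secondary outcome; the primary outcome, severe hypoglycemia, has no expected rate, target difference or power

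*Protocol*

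**What the plan says.** The Protocol Synopsis (section 2.0) gives the primary outcome as "rate of severe hypoglycemia". Under secondary outcomes it lists "wound infection day 7; and day 30 (clinic follow-up)".

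The NUMBER OF SUBJECTS entry of the same Synopsis assumes that "6% of the participants receiving boluses will acquire a wound infection and 1% of the participants receiving insulin drip will acquire an infection". With a two-sided alpha of 0.05 it concludes that "to have power = 80% to detect the difference, you need to enroll 192 participants per group", 384 in total.

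The other statements on size name no outcome:

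- Synopsis, Rationale for Number of Subjects, and section 7.3, in the same words: "Sample size calculated basis of a two-sided test and an alpha = 0.05, to have power = 80%".
- Section 7.1: "This study will include a total of 384 adult patients randomly assigned to each arm (192 per arm)".

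For the analysis, section 7.3 says "Using relative risk for statistical analysis and log rank", with significance at P below 0.05. The protocol nowhere gives an expected rate, a target difference or a power for severe hypoglycemia.

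**The concern.** A power statement belongs to the outcome whose rates went into it. Here those rates are for wound infection. A reader of section 7 alone, where no outcome is named, would take the 80% as the power of the primary comparison, which it is not.

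Severe hypoglycemia may well be uncommon in this trial, and the protocol gives no reason to expect a high rate: it excludes patients with hypoglycemic events in the previous 6 months. If the rate is about 5% or less and the effect about two-fold, the primary test is more likely than not to be non-significant even though the difference is real. The named effect measure is the relative risk. With few events, a non-significant result would bound the absolute difference but leave the relative risk wide open. For a primary outcome that is a safety event, such a result could easily be taken as reassurance that the data do not support.

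**Working it through.** **Inputs from the protocol.** Wound infection 6% (boluses) v 1% (drip); two-sided alpha 0.05; power 80%; 192 per group (Synopsis, NUMBER OF SUBJECTS; section 7.1). Severe hypoglycemia: no rate and no difference given.

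**Step 1: reproduce 192 for wound infection.** The likelihood-ratio formula for two proportions is

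n per group = (z₀.₉₇₅ + z₀.₈₀)² / {2[l(p₁) + l(p₂) − 2l(p̄)]}, where l(p) = p ln p + (1 − p) ln(1 − p).

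With p₁ = 0.06, p₂ = 0.01 and p̄ = 0.035:

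- (1.960 + 0.842)² = 7.849
- l(0.06) = −0.22697; l(0.01) = −0.05600; l(0.035) = −0.15171
- bracket = −0.22697 − 0.05600 + 2 × 0.15171 = 0.02046 (from unrounded values)
- n = 7.849 / (2 × 0.02046) = 191.8, so 192

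The exact power of the uncorrected chi-square test at 192 per group, from binomial probabilities summed over all 2×2 tables, is 80.9%. The common pooled-variance formula gives 211, so the result depends somewhat on the method, but 192 is a legitimate answer for 6% v 1%. The 80% is the power for wound infection.

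**Step 2: what 192 per group offers for severe hypoglycemia.** All rates below are assumptions. They treat the outcome as the proportion of patients with at least one event. Power is exact, for the uncorrected chi-square test at two-sided 0.05. Patients per arm come from the pooled-variance formula

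n = {z₀.₉₇₅ √[2p̄(1 − p̄)] + z₀.₈₀ √[p₁(1 − p₁) + p₂(1 − p₂)]}² / (p₁ − p₂)².

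| Assumed rates (a doubling) | Power at 192 per arm | Patients per arm for 80% power |
|---|---|---|
| 1% v 2% | 11% | 2,319 |
| 2% v 4% | 20% | 1,141 |
| 3% v 6% | 29% | not computed |
| 5% v 10% | 47% | 435 |
| 10% v 20% | 79% | 199 |

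The two right-hand columns use different methods, and the pooled formula is slightly more demanding (211 against 192 for 6% v 1%). The last column therefore shows order of magnitude only.

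**Step 3: smallest worse-arm rate detectable with 80% power at 192 per arm** (same exact test, rates searched in steps of 0.1 point, rounded here):

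| Better arm | Worse arm | Relative risk |
|---|---|---|
| 1% | 6% | 6 |
| 2% | 8% | 4 |
| 5% | 13% | 2.6 |
| 10% | about 20% (20.2%) | 2 |

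**Step 4: what a null result would look like.** 95% intervals when both arms of 192 have the same number of events (Newcombe for the risk difference, log method for the relative risk):

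- 2 v 2 events: SE(ln RR) = √(2/2 − 2/192) = 0.995; RR 0.14 to 7.0; difference −2.8 to +2.8 points.
- 10 v 10 events: SE(ln RR) = √(2/10 − 2/192) = 0.435; RR 0.43 to 2.35; difference −4.7 to +4.7 points.

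**The case against.** The strongest objection is that severe hypoglycemia may not be the intended primary outcome at all. The Synopsis gives intraoperative glucose control as the primary objective and puts hypoglycemic events under the secondary objectives. If the label is the slip, a power table for hypoglycemia answers the wrong question, and the first repair is to settle the primary outcome. This stands as a related inconsistency and strengthens the case for realigning the outcome. It does not rescue the 80%, because the protocol as written calls severe hypoglycemia primary and sizes the trial on something else.

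A second objection concerns method. The protocol does not define the unit of analysis, and it also names a log-rank test. The detectable rates hold for one binary outcome per patient and an uncorrected chi-square test; with a continuity correction, the power for 1% v 6%, 2% v 8% and 5% v 13% falls to 71%, 73% and 74%. That is fair, and any such figures placed in the protocol should name the test. The correction makes the power lower, so it does not weaken the point.

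Third, the protocol claims no equivalence or non-inferiority, so a warning about reading a null result as equal safety answers a claim it does not make. That is true of the text. The sentence is a precaution and secondary to the main correction.

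An unseen statistical analysis plan does not remove the problem, because the protocol itself fixes the primary outcome, the sample size and the assumptions behind it.

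**Conclusion.** The concern holds and must be fixed. The 192 per group and 80% power are correct for wound infection at 6% v 1%, a secondary outcome, and say nothing about the primary one. The power for severe hypoglycemia cannot be derived from the protocol. For a doubling, under assumed rates from 1% v 2% to 5% v 10%, it runs from 11% to 47%. It comes close to 80% only if the event is as common as about 10% v 20%, or if the effect is much larger than two-fold, such as six-fold from 1%. These figures assume one binary outcome per patient, 192 analysed per arm and the uncorrected chi-square test. It is therefore not shown that the trial is underpowered for its primary outcome; what is shown is that its power is unknown and that the stated figure does not apply.

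**What to change.** Choose one of two routes.

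1. **Keep severe hypoglycemia primary and correct the power statement.** In the Synopsis and in sections 7.1 and 7.3, say that 192 per group and 80% power refer to wound infection, a secondary outcome. Beside it, state what 384 patients can detect with 80% power for severe hypoglycemia: 1% v 6%, 2% v 8%, 5% v 13% and 10% v about 20%. Label these as assumptions and name the test and the unit of analysis, or replace them with a rate that the investigators justify. State that severe hypoglycemia will be reported as a risk difference and a relative risk, each with a 95% confidence interval, and that a non-significant result will not be read as equal safety.

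2. **Align the primary outcome with the outcome used for the sample size.** This also gives the opportunity to reconcile the primary outcome with the primary objective. It is a change of primary outcome, so it needs an amendment with ethics approval before it takes effect (section 9.1). It should be settled before anyone sees outcome data by arm, which matters because interim analyses are planned throughout the hospital stay and at each visit.

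Neither route needs extra patients. The first costs protocol wording and a less favourable stated power for the primary outcome; the second costs the amendment. Keeping severe hypoglycemia primary and also powering it would need more patients unless the rate or the effect is large: for example, 435 per arm for 5% v 10%, against 192 now.

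### Does 192 per group fall short of the stated 80% power because the protocol analyses a relative risk?

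*Protocol*

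**What the plan says.** Under NUMBER OF SUBJECTS in the Synopsis (2.0), the protocol assumes that "6% of the participants receiving boluses will acquire a wound infection" and that "1% of the participants receiving insulin drip will acquire an infection". With a two-sided alpha of 0.05, the result is stated as: "to have power = 80% to detect the difference, you need to enroll 192 participants per group for a total of 384 participants". Section 7.1 repeats 384 in total and 192 per arm. No test or formula is named for this calculation.

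The analysis is described in the Synopsis (STATISTICS), in 3.0 (Statistical analysis) and in 7.3, each time in one sentence: "Using relative risk for statistical analysis and log rank". The significance level is P < 0.05. No method for the p-value of the relative risk, no interval method and no rule for empty cells is given. Section 3.0 makes the bolus group the control, so the relative risk is drip over bolus.

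**The concern.** A colleague checking 192 with the usual textbook formulas does not get it back. The unpooled formula gives 209 per group, the pooled formula 211, the continuity-corrected formula 250 and the log relative risk formula 281. All exceed 192, and since the protocol names relative risk, the last looks the most relevant.

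The expected counts add to the worry. At 1% the drip group expects 192 × 0.01 = 1.9 infections, so a trial with none is quite likely, and the log relative risk cannot then be computed. If the 80% held only for an analysis other than the one named, the trial would be underpowered by about 9 points on the protocol's own assumptions. The main estimate could also fail in just those trials where the drip did best.

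**Working it through.** **Inputs (Synopsis 2.0):** p1 = 0.06 (bolus), p2 = 0.01 (drip), two-sided alpha 0.05 (z = 1.960), power 80% (z = 0.842), n = 192 per group. An exact 192/192 split is used.

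**1. Reproduce the stated figure.** Take every pair of infection counts from two binomials with n = 192. Compute the uncorrected Pearson statistic z = |x1 − x2|/n ÷ √(2p̄(1 − p̄)/n), where p̄ = (x1 + x2)/(2n), and add the probabilities of all pairs with z > 1.960.

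| n per group | Exact Pearson power |
|---|---|
| 188 | 79.98% |
| 190 | 80.5% |
| 192 | 80.9% |

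The first n to reach 80% is 189. With a common rate of 3.5% in both groups, the test's actual error rate at 192 per group is 4.9%, so this power is not bought with an inflated alpha.

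**2. Why the closed formulas differ.**
- Unpooled: (1.960 + 0.842)² × (0.06 × 0.94 + 0.01 × 0.99) ÷ 0.05² = 208.2.
- Pooled: (1.960√(2 × 0.035 × 0.965) + 0.842√(0.0564 + 0.0099))² ÷ 0.05² = 210.9.
- Log relative risk: (1.960 + 0.842)² × (0.94/0.06 + 0.99/0.01) ÷ (ln 6)² = 280.3.
- Arcsine: 2 × (1.960 + 0.842)² ÷ 0.2946² = 180.9, where 0.2946 = 2 arcsin√0.06 − 2 arcsin√0.01.

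These are large-sample approximations, applied here with 1.9 expected events in one group, and they fall on both sides of 192. The pooled formula approximates the same Pearson test as step 1. It puts power at 76.2% where the exact value is 80.9%, so the approximation is what is off.

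**3. Power at 192 per group by choice of test (exact enumeration).**

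| Test | Power |
|---|---|
| Likelihood ratio | 84.2% |
| Pearson, uncorrected | 80.9% |
| Fisher, or continuity-corrected chi-square | 71.1% |
| Wald on log relative risk, 0.5 added in zero cells | 71.2% |
| Wald on log relative risk, zero-cell trials not significant | 59.3% |

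The likelihood-ratio test's actual error rate at a common 3.5% is 6.1%, so part of its extra power is not real. The 0.5-corrected Wald test runs at 2.9%, which explains much of its low power.

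**4. Log rank.** This is the only hypothesis test that the analysis sections name. Simulation with the same rates and complete 30-day follow-up gives about 80.7%.

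**5. No infection in the drip group.** The probability is 0.99^192 = 14.5%, or 1 in 6.9. The relative risk is then 0 ÷ (bolus risk) = 0, a defined value as long as the bolus group has an event. The log relative risk and its Wald interval are not defined. The Pearson test still works: with 0 against 4 infections, z = (4/192) ÷ √((4/384)(380/384)(2/192)) = 2.01, which is significant. Four or more bolus infections occur with probability 99.7% at a 6% rate.

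**The case for a change.** The strongest case for the concern is that the protocol both promises a power and names an analysis, so the two ought to match. No chi-square test is mentioned anywhere. Every Wald version on the log relative risk stays below 80%: it reaches only 73.8% even if all trials with no drip infection are counted as significant. The choice can also change a conclusion. With 0 drip and 8 bolus infections, Pearson rejects while the 0.5-corrected Wald test does not, since it needs 9. Finally, 192 is both the number required and the number enrolled. With an assumed loss of 5% or 10% by day 30 (about 182 or 173 per group), Pearson power is 78.5% or 76.0%.

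The arithmetic in this case stands. What does not follow is that the stated 80% is wrong. The 71% needs a Wald test, a log scale and a 0.5 correction, none of which the protocol states. A different zero-cell rule gives 59.3%, so the figure depends on what is added to the text. Reporting a relative risk with a chi-square p-value fits the protocol's words equally well and delivers the stated power. The accompanying test, the interval method and a zero-cell rule are commonly left to the SAP, which is not at hand. The loss rates are assumptions with no figure in the protocol behind them, and they cost 2 to 5 points under the Pearson test.

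**Conclusion.** The concern does not hold. On the protocol's own inputs, 192 per group gives 80.9% power with an uncorrected Pearson chi-square and about 80.7% with the log rank, so the stated 80% is reproduced. The shortfall to 71% belongs to one unstated way of testing a relative risk. The relative risk itself is not undefined in 1 trial in 7. In those trials it equals 0, and only the log-scale Wald interval fails.

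This rests on the assumed 6% and 1%, a 192/192 split (the protocol uses simple randomization, so the realised split may differ somewhat) and complete follow-up to day 30. The margin is thin, at 3 patients per group above the 189 that suffice, so appreciable loss would take power slightly below 80%.

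The conclusion covers only the arithmetic for wound infection. That the Synopsis lists wound infection as a secondary outcome, with severe hypoglycemia as primary, is a separate question which this check does not settle.
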